#### **Treatment-Related Treatment-Emergent Adverse Events**

Every AE will be assessed by the investigator for its relationship to the randomly assigned study medication. The subset of TEAEs considered by the investigator as either possibly, probably, or definitely related to study treatment will be summarized as drug-related TEAEs by SOC and PT.

#### Treatment-Emergent Adverse Events by Maximal Severity

Every AE will be graded by the investigator as mild, moderate, or severe, so for each patient the greatest severity observed can be obtained by comparing the severity of all of a patient's TEAEs that share the same SOC or PT. A table of TEAEs by maximal severity will be prepared for each treatment arm by SOC and PT.

#### **Treatment-Emergent (Not Including Serious) Adverse Events**

The most common non-serious TEAEs will be summarized. All PT that occur in at least 5% of the Safety Population patients in any treatment group, when not counting the serious TEAEs, will be tabulated by SOC and PT for each treatment group. These reports will also present the total number of TEAEs for each SOC and PT.

#### **Treatment-Emergent Adverse Events of Special Interest**

The TEAEs of special interest – with preferred terms grouped in the categories of dizziness, nausea, and vomiting – will be identified prior to unblinding and summarized. This summary will also present the total number of TEAEs for each category and PT.

#### 6.3. Clinical Laboratory Analyses

At each time point, the change from baseline will be derived for each numeric laboratory parameter. Descriptive statistics for the value of each parameter at each time point and the change from baseline for each parameter at each post-dose time point will be provided by treatment group. A 95% confidence interval for the change from baseline will be computed for each treatment group using a large-sample T-statistic approximation; the Normality assumption will not be checked.

The number of patients discontinued due to abnormal liver laboratory assessments will be summarized.

# 6.4. Vital Signs and Weight

At each time point, the change from baseline will be derived for each numeric vital sign parameter. Descriptive statistics for the value of each parameter at each time point and the change from baseline for each parameter at each post-dose time point will be provided by treatment group.

## 6.5. Electrocardiograms

At each time point, the change from baseline will be derived for each numeric ECG parameter. Descriptive statistics for the value of each parameter at each time point and the change from baseline for each parameter at each post-dose time point will be provided by treatment group.

The number (percent) of patients who have an extreme QTcF value at any time while on treatment will be tabulated by treatment group. Extreme QTcF values will be determined using the following criteria:

- QTcF  $\geq$  500 msec
- QTcF  $\geq$  550 msec
- Change from baseline in  $QTcF \ge 30$  msec
- Change from baseline in  $QTcF \ge 60$  msec.

All on-treatment values, including unscheduled assessments, will be considered.

## 6.6. Other Safety Analyses

Gait and balance will be assessed with the Timed Up and Go (TUG) test. At each time point, the change from baseline will be derived for the time to perform the task. Descriptive statistics for the value at each time point and the change from baseline at each post-dose time point will be provided by treatment group.

The number of patients with any post-baseline clinically significant results of physical or neurological exams will be summarized. Any data captured by the C-SSRS will be included in by-patient listings.

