The most common AEs reported in the 3 clinical studies were (in order of decreasing frequency): dizziness, vomiting, nausea, tiredness, and headache. In the MAD study, vomiting appeared to be a "first-dose" effect for most subjects (1 subject also had an episode of vomiting on Day 2, which did not recur with continued dosing). Nausea also tended to occur during the first 3 days of dosing, whereas dizziness tended to be reported later during dosing and at higher MP-101 doses (150 and 250 mg), but nausea did not persist with ongoing dosing. There were no significant changes in vital signs (blood pressure [BP] and heart rate), electrocardiograms (ECGs; including corrected QT interval [QTc]), and safety laboratory tests (biochemistry, hematology, and urinalysis) in subjects receiving MP-101.

To date, there have been no adverse drug reactions associated with administration of MP-101 in healthy subjects, for which AEs were mild (summarized above). In an elderly patient population with dementia-related psychosis and agitation/aggression, the mild AEs reported in healthy subjects may present a greater safety concern. Adverse events include reports of dizziness which could lead to gait instability and falls in an elderly dementia population. The risk for gait

instability will be assessed for ambulatory patients throughout Study MP-101-01 with the Timed Up and Go (TUG) test. Similarly, transient vomiting, unrelated to the dose, was reported in healthy subjects in the SAD and MAD studies. There is a greater risk of dehydration or aspiration in dementia patients. To improve patient safety, MP-101 exposure will be reduced in Study MP-101-01 (60-mg maximal dose in dementia patients vs. 400-mg QD dose in healthy subjects).

More detailed information about the known and expected benefits, risks, serious adverse events (SAEs), and reasonably anticipated AEs of MP-101 can be found in the Investigator's Brochure (IB).

4. Objectives and Endpoints

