9.4. Safety

9.4.1. Physical and Neurological Examination

Physical and neurological examinations will be conducted according to the Schedule of Activities (Section 2) and as clinically indicated.

Body weight and height will be recorded. Physical examinations will include assessment of general appearance, skin, head and neck, lymph nodes, thyroid, abdomen (bowel sounds and liver and spleen palpation), back (costovertebral angle tenderness), and musculoskeletal, cardiovascular, and respiratory systems. Neurological examinations will include assessment of mental status, cranial nerves, muscle strength, tone, and bulk, motor and sensory systems, muscle stretch reflexes, coordination, and balance and gait. Gait and balance will be assessed with the TUG test (Appendix 5) for ambulatory patients. The physical and neurological examination will be performed by a physician, nurse practitioner, or physician's assistant holding appropriate delegation.

If a clinically meaningful change is noted during the study, an additional full neurological examination will be performed as soon as possible, along with any other medical follow-up deemed necessary by the investigator.

Any clinically significant change from baseline (Visit 2 [Week 0]) on follow-up physical and neurological examinations should be reported to Mediti Pharma, Inc. or its designee as an AE via CRF.

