## 8. **REPORTING CONVENTIONS**

The following conventions will be applied to all data presentations and analyses:

- Continuous variables will generally be summarized by the number of patients, mean, standard deviation, median, minimum, and maximum.
- Categorical variables will be summarized by the number and percentage of patients within each category.
- All mean and median values will be formatted to one more decimal place than the measured value.
- Standard deviation values will be formatted to two more decimal places than the measured value.
- Minimum and maximum values will be presented with the same number of decimal places as the measured value.
- The number and percent of responses will be presented in the form XX (XX %), where the percentage is in parentheses. Percentages will be rounded to the nearest percent. In the case of a frequency of zero, the frequency and percentage will be presented as 0 rather than 0 (0%).
- All summary tables will include the analysis population sample size (i.e. number of patients) in each treatment group.
- Date variables will be formatted as ddMMMYY for presentation.

For PK data, the geometric coefficient of variation will be calculated assuming the data follow a log-Normal distribution. That is, let X = concentration.

If Y = log[X] has a Normal distribution with

 $E[Y] = \mu$  and  $Var[Y] = \sigma^2$ ,

then X has a log-Normal distribution with

 $E[X] = exp[\mu + .5*\sigma^2] = exp[\mu]*exp[.5*\sigma^2]$ 

Compound: MP-101 Protocol: MP-101-01(b)

and

$$Var[X] = exp[2\mu + 2*\sigma^{2}] - exp[2\mu + \sigma^{2}] = exp[2\mu]*exp[\sigma^{2}]*(exp[\sigma^{2}] - 1)$$

so

$$SD[X] = exp[\mu] * exp[.5*\sigma^2] * sqrt(exp[\sigma^2] - 1)$$

Therefore,  $CV[X] = SD[X]/E[X] = sqrt(exp[\sigma^2] - 1)$ . The log-transformed concentration values will be computed and the coefficient of variation calculated using the sample variance.

	Screen	Treatment Period (10 Weeks)								
Visit Number	V1	V2	V3	V4	V5	V6	V7	V8	V9	гт
Week	-1 to -5	0	1	2	4	6	8	10	11	E I
Days from Randomization (target)	-1 to-35	0	7	14	28	42	56	70	77	
Visit Window (± days from target)				2	2	2		2	2	
Study site visit	Х	Х		Х	х	х		х	х	Х
Informed Consent	v									
(before any procedures/tests)	А									
Clinical Assessments										
Demographics, height	х									
Weight	х	х		х	x	x		х	х	х
Vital signs (BP and pulse)	х	Х		х	х	х		х	х	х
Medical history and physical exam	Х									
Neurological exams	Х	Х						Х		Х
TUG (if applicable)	х	Х		Х	х	х		Х	х	

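### The TUG summary covers only patients with a recorded time, and falls and gait terms are not grouped, so a gait signal can be understated

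*SAP*

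**What the plan says.** - **TUG analysis.** SAP 6.6: "At each time point, the change from baseline will be derived for the time to perform the task". Then: "Descriptive statistics for the value at each time point and the change from baseline at each post-dose time point will be provided", by arm. SAP 8 sets what is shown: "Continuous variables will generally be summarized by the number of patients, mean, standard deviation, median, minimum, and maximum". Neither section has a category for a patient who can no longer do the test, a cut-off, or a summary of why a test is missing. SAP 2.7 deals with missing dates and missing NPI response only.
- **Second gait-related item.** SAP 6.6 also states: "The number of patients with any post-baseline clinically significant results of physical or neurological exams will be summarized". Per Protocol 9.4.1 that examination includes gait: "coordination, and balance and gait. Gait and balance will be assessed with the TUG test".
- **Events of special interest.** SAP 6.2 defines them "with preferred terms grouped in the categories of dizziness, nausea, and vomiting". There is no falls, gait or balance category.
- **The risk named in the protocol.** Section 3 (Introduction) refers to "dizziness which could lead to gait instability and falls in an elderly dementia population" and gives TUG as the means of following it. The same section names dehydration and aspiration as greater risks of vomiting in these patients.
- **Who has a TUG, and when.** Inclusion criterion [2] sets an entry limit of 30 seconds and exempts wheelchair users. Both schedules mark TUG at Visits 1, 2, 4, 5, 6, 8 and 9 and leave the early termination cell empty. The neurological examination is marked at Visits 1, 2 and 8 and at early termination.

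**The concern.** TUG is a performance test, so the reason for a missing value can be the very harm being measured. Someone who loses the ability to walk unaided by another person, or who leaves the study because of dizziness and unsteadiness, contributes no time. The remaining patients define the mean, the median and the maximum. If MP-101 affects gait, the loss could be heavier in that arm, and the comparison would then lean towards showing no effect.

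The adverse event side does not fully make up for this. Falls, gait disturbance and balance problems may be coded to different preferred terms. With about 50 patients per arm, each term may have only one or two patients, and no planned row adds them together as a gait outcome. At stake is how readily a reader of the study report could see a gait problem that the protocol itself anticipated.

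**Working it through.** The documents give no TUG standard deviation, failure rate or fall rate, so there is no planned figure to reproduce. The check is a reading of the plan followed by an illustration under stated assumptions.

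**1. Routes by which a patient leaves the TUG table**

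- Visit 3 is a telephone call, so the first scheduled TUG on treatment is at Visit 4. Protocol 7.4 has patients intolerant of the first two dose steps leaving the study before then, with dizziness given as an example of intolerance. TUG is not marked at early termination. Such patients have no scheduled post-baseline TUG.
- Protocol 8.1.1 foresees stopping product for vomiting or dizziness with gait instability on TUG.
- Per Protocol 9.4.1, "Gait and balance will be assessed with the TUG test (Appendix 5) for ambulatory patients". A patient who stops being ambulatory on treatment therefore has no time.
- SAP 2.6 analyses by nominal visit, so a TUG done at an unscheduled visit has no row in a by-visit table. SAP 6.5 handles QTcF differently: it counts patients crossing limits and includes unscheduled values.

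**2. Size of the possible understatement (assumed inputs)**

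Let N be the patients in an arm, k the number who worsen by d seconds and then have no value, and m the mean change in the rest.

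- Mean shown in the table: m
- Mean over all patients: [k·d + (N − k)·m] / N
- Understatement: (k/N)·(d − m)

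Take N = 50 (half of the planned 100; fewer if some are wheelchair users) and m = 0.

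| k | d (s) | Table shows | n shown | All-patient mean | Count as % of 50 |
|---|---|---|---|---|---|
| 2 | 10 | 0 s | 48 | 2×10/50 = 0.4 s | 4% |
| 2 | 20 | 0 s | 48 | 2×20/50 = 0.8 s | 4% |
| 5 | 10 | 0 s | 45 | 5×10/50 = 1.0 s | 10% |
| 5 | 20 | 0 s | 45 | 5×20/50 = 2.0 s | 10% |
| 10 | 10 | 0 s | 40 | 10×10/50 = 2.0 s | 20% |
| 10 | 20 | 0 s | 40 | 10×20/50 = 4.0 s | 20% |

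SAP 1.4 expects 20% drop-out per arm before Week 4, which is 0.20 × 50 = 10 patients for all reasons together. As a picture of early withdrawal alone, k = 10 would mean that every one of them was a gait case, so the bottom rows are extreme. The choice m = 0 enters only through d − m. With m = 2, k = 5 and d = 20, the understatement is (5/50)×18 = 1.8 s instead of 2.0 s.

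**3. What the adverse event tables would show**

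At assumed fall rates of 2%, 5% and 10%, the chance of at least one faller among 50 patients, 1 − (1 − p)^50, is 64%, 92% and 99%. Each fall reported as an event enters the general tables.

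Seeing a difference between arms is harder. The SAP plans no tests on adverse events, but as a yardstick only, a one-sided 5% Fisher test with 50 per arm has power of 13% for 5% against 10%, 39% for 5% against 15%, and 66% for 5% against 20%. Splitting one gait outcome over several preferred terms makes each row smaller still.

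**The case against.** A reader might infer that gait is analysed only through the mean TUG time and that the harm can drop out of the results. The documents do not support this:

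- The planned table also gives n, median and maximum. Attrition is visible in n, and a very slow patient shows in the maximum.
- SAP 6.6 counts clinically significant neurological findings. That examination covers gait and is scheduled at early termination. Protocol 9.4.1 also requires such changes to be reported as adverse events.
- A reported fall stays in the treatment-emergent tables, in the serious event table if serious, and in the discontinuation table and listing if it led to stopping. A patient is counted once per organ class, so terms within one class are combined.
- Appendix 5 sets no time limit and allows the usual gait aid and rests. Slow or unsteady patients who can still walk get a long time, which raises the mean. Only inability or a missed test loses the value.

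Nor does the SAP contradict the protocol on special interest. The synopsis gives the same three examples, and Protocol 8.1.1 and 9.4.6 speak of vomiting or dizziness. The protocol does not rank falls above its other concerns.

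The choice of 30 seconds is also open to question. It is an entry limit, not a defined outcome: moving from 29 to 31 seconds would count, and from 10 to 28 would not. Appendix 5 also lists more than 14 seconds as a marker of fall risk in one group.

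All of this stands, and it limits the point without removing it. The median and maximum describe the same remaining patients as the mean. A falling n is unexplained. The examination count pools every physical and neurological finding, and after baseline the neurological examination is scheduled only at Visit 8 and early termination. An organ class row mixes gait terms with everything else in that class, and the documents do not say that falls, gait and balance terms share one.

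**Conclusion.** The point holds in a limited form. The TUG summary has no place for patients who become unable to do the test, and falls, gait and balance terms are not brought together. A gait signal can therefore be understated in one table and scattered in the others. It can be understated, not lost: individual reported events remain visible.

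The range of 0.4 to 4.0 s against 0 s rests wholly on the assumed k, d and m, and is not a forecast. The direction towards understatement assumes that patients without a value have worsened more than those with one (d greater than m). That is plausible given the withdrawal routes in the protocol, but it is not shown by any data in the documents. Whether the eCRF or the companion document of table formats already records inability to do TUG cannot be seen. The primary analysis is not affected.

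**What to change.** - **SAP 6.6.** Keep the planned TUG statistics. Beside them, among patients ambulatory at baseline, tabulate by arm the number and percent with either TUG not done because no longer able, or any post-baseline TUG over 30 seconds. Count unscheduled values, as SAP 6.5 does for QTcF. Present 30 seconds as one descriptive cut-off taken from the entry criterion, not as the main gait outcome. Report the reasons for missing TUG by arm.
- **SAP 6.2.** Add a special-interest grouping of falls, gait and balance terms, and one of dehydration and aspiration terms, with the preferred terms fixed before unblinding.
- **Schedules.** Reconcile the empty TUG cell at early termination with Protocol 9.4.1, which uses TUG to assess gait and balance, while the neurological examination is marked at that visit.

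Cost: a few sentences of SAP text, two extra descriptive tables, and one eCRF field for the reason TUG was not done if none exists. For patients already past their visits, the reason may have to be recovered by query.

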6.1. Inclusion Criteria

Patients are eligible for inclusion in the study only if they meet all of the following criteria at screening:

Type of Patient – Patient and Disease Characteristics

[1] Males or females (of non-childbearing potential) \geq 50 years of age

Note: Females of non-childbearing potential are defined as women ≥60 years of age, postmenopausal women ≥50 and <60 years of age who have had a cessation of menses for at least 12 months, or women who are congenitally or surgically sterile (i.e., have had a hysterectomy or bilateral oophorectomy or tubal ligation).

To confirm postmenopausal status for women ≥50 and <60 years of age who have had a cessation of menses for at least 12 months, follicle stimulating hormone levels will be assessed and must be ≥40 mIU/mL.

Note: Males must agree to use 2 forms of highly effective birth control (see below) with female partners of childbearing potential while enrolled in the study, and for at least 28 days following the last dose of investigational product.

The following birth control methods are considered highly effective:

- Oral, injectable, or implanted hormonal contraceptives
- Condom with a spermicidal foam, gel, film, cream, or suppository
- Occlusive cap (diaphragm or cervical/vault caps) with a spermicidal foam, gel, film, cream, or suppository
- Intrauterine device
- Intrauterine system (e.g., progestin-releasing coil)
- Vasectomized male (with appropriate postvasectomy documentation of the absence of sperm in the ejaculate).
- [2] Ambulatory (with or without walking device) with a stable gait as assessed with a TUG test (Okumiya et al. 1998; Nordin et al. 2006) that must be completed in

- \leq 30 seconds. The test may be repeated once with instruction. Patients in wheelchairs are also eligible and do not need to complete the TUG test.
- [3] Have an MMSE score of 10 to 24.
- [4] Meets clinical criteria for one of the following disorders: dementia associated with Parkinson's disease, dementia with Lewy bodies, possible or probable Alzheimer's disease, frontotemporal degeneration spectrum disorders, vascular dementia.
- [5] Must be able to communicate verbally.
- [6] At Visit 1 (screening) and Visit 2 (Week 0) have at least ONE of the following:
 - o an NPI score of ≥ 4 on either delusions or hallucinations individual items
 - o an NPI score of ≥6 on the Psychosis Subscale (combined delusions and hallucinations)
 - o an NPI score of ≥4 on agitation/aggression domain

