10.3.4. Safety Analyses

10.3.4.1. Adverse Events

All investigational product and protocol procedure AEs will be listed, and if the frequency of events allows, safety data will be summarized using descriptive methodology.

The incidence of symptoms for each treatment will be presented by severity and by association with investigational product as perceived by the investigator. Symptoms reported to occur prior to enrollment will be distinguished from those reported as new or increased in severity during the study. Each symptom will be classified by the most suitable term from the most current version of Medical Dictionary for Regulatory Activities (MedDRA).

The number of investigational product-related SAEs will be reported.

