10.3.4.2. Other Evaluations of Safety

Other safety parameters that will be assessed include physical/neurological examinations, safety clinical laboratory parameters, vital signs, and ECG parameters. The parameters will be listed and summarized using standard descriptive statistics. Additional analysis will be performed if warranted upon review of the data.

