## 2.5. Definition of Baseline Assessments

Day 0 (Week 0) is defined in this study as the day of Visit 2. The last assessment made before the first dose of study drug will be defined as the Baseline assessment. This should include all assessments made on or before Day 0. Adverse events that occurred on Day 0 will be assumed to be treatment-emergent, unless the eCRF records that the event started prior to the first dose of study drug.

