#### **Treatment-Emergent Adverse Events**

Treatment-emergent adverse events (TEAE) include all adverse events that emerge or worsen after taking the first dose of study drug. TEAEs will be summarized for each treatment group by SOC and PT, and by PT in order of decreasing frequency of MP-101 preferred term.

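### SAP 6.6 counts clinically significant physical or neurological findings without reference to baseline, so this one descriptive safety table mixes persisting entry abnormalities with new or worsened ones

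*SAP*

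**What the plan says.** The SAP's rule for the examinations is one sentence in section 6.6: "The number of patients with any post-baseline clinically significant results of physical or neurological exams will be summarized". It sets no condition on what the baseline examination showed, and it does not say that the count is split by treatment group.

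Other parts of the plan bear on the same data:

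- SAP 2.5 supplies a usable baseline: "The last assessment made before the first dose of study drug will be defined as the Baseline assessment". The examination rule does not use it.
- SAP 6.6 itself derives change from baseline for the Timed Up and Go (TUG) test, by treatment group. SAP 6.3, 6.4 and 6.5 do the same for laboratory values, vital signs and ECG.
- Protocol 9.4.1 makes change the trigger for adverse event reporting: "Any clinically significant change from baseline (Visit 2 [Week 0]) on follow-up physical and neurological examinations should be reported" as an adverse event.
- SAP 6.2 tabulates treatment-emergent events by treatment group. These "include all adverse events that emerge or worsen after taking the first dose of study drug".
- Protocol 10.3.4.1 separates old from new symptoms: "Symptoms reported to occur prior to enrollment will be distinguished from those reported as new or increased in severity during the study".
- Protocol 10.3.4.2 covers the analysis of the examinations, along with laboratory, vital-sign and ECG data: "The parameters will be listed and summarized using standard descriptive statistics".

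**The concern.** The examination is broad and the population has neurological disease at entry. Protocol 9.4.1 states: "Neurological examinations will include assessment of mental status, cranial nerves, muscle strength, tone, and bulk, motor and sensory systems", and goes on to coordination, balance and gait. Every patient has dementia; one inclusion criterion is "Have an MMSE score of 10 to 24". Parkinson's disease dementia and Lewy body dementia qualify, and patients in wheelchairs are eligible. Some patients may therefore enter with findings in the domains examined.

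If such a finding is rated clinically significant again after baseline, the patient is counted in SAP 6.6 exactly as one with a new finding. What is at stake is whether this table can be interpreted. Protocol section 3 names dizziness leading to gait instability and falls as a concern. The neurological examination also reaches patients whom TUG does not: those in wheelchairs, and those seen at early termination, where the schedule has a neurological examination but no TUG. A count that partly reflects the disease mix at entry is a weak cross-check on the adverse event tables and cannot be reconciled with them.

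**Working it through.** **Step 1: the rules applied to three hypothetical records.** Assume that each finding is rated clinically significant wherever it is present, and that the worsening in record 3 is itself clinically significant.

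| Record | Visit 2 | Visit 8 | SAP 6.6 count | AE report under Protocol 9.4.1, then TEAE table |
|---|---|---|---|---|
| 1 | Rigidity and abnormal gait | Unchanged | Yes | No |
| 2 | Normal gait | New ataxia | Yes | Yes |
| 3 | Abnormal gait | Clearly worse | Yes | Yes |

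The SAP 6.6 count cannot tell record 1 from records 2 and 3. The adverse event route can.

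**Step 2: size of the dilution.** The documents give no figure to reproduce, so this is an illustration on assumed inputs:

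- new-finding rate q among patients with no baseline finding: 5% on placebo, 15% on MP-101 (10 points apart);
- share b of each arm with a baseline finding: 0 to 95%;
- every baseline finding persists and is rated significant again.

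The share counted is b + (1 − b) × q, so the difference between arms is (1 − b) × (15% − 5%).

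| b | Placebo | MP-101 | Difference (points) |
|---|---|---|---|
| 0% | 5.0% | 15.0% | 10.0 |
| 10% | 14.5% | 23.5% | 9.0 |
| 30% | 33.5% | 40.5% | 7.0 |
| 50% | 52.5% | 57.5% | 5.0 |
| 80% | 81.0% | 83.0% | 2.0 |
| 95% | 95.25% | 95.75% | 0.5 |

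For example, at b = 30% placebo is 0.30 + 0.70 × 0.05 = 0.335 and MP-101 is 0.30 + 0.70 × 0.15 = 0.405.

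**Step 3: chance imbalance at entry.** About 100 patients randomized 1:1 gives about 50 per arm. The standard deviation of the chance difference in b between arms is √(2b(1 − b)/50). At b = 30% this is √(0.42/50) = 9.2 points; at 50%, √(0.50/50) = 10.0; at 80%, √(0.32/50) = 8.0. These exceed the remaining differences of 7, 5 and 2 points. At b = 10% it is √(0.18/50) = 6.0 points, below the remaining 9. This is noise around zero, not a shift in one direction.

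**Step 4: feasibility.** The schedule places neurological examinations at Visits 1, 2 and 8 and at early termination. The full physical examination is at Visit 1, with symptom-directed examinations from Visit 2. A comparison with baseline needs no new data.

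**The case against.** The strongest reply is that the safety evaluation does not depend on this table. A reader might infer from SAP 6.6 that new neurological findings on MP-101 would be hidden. The documents do not support that. Clinically significant changes from Visit 2 are to be reported as adverse events, and events that emerge or worsen are tabulated by treatment group, with a further table by maximal severity. Gait has its own change-from-baseline analysis through TUG. UPDRS Part III is a named safety endpoint, and dizziness is a category of special interest. This part of the reply stands and limits the point to one display. What it leaves open is that adverse event capture depends on the investigator filing a separate report, so an interpretable examination table is still useful as a check.

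A reader might also infer that SAP 6.6 contradicts an endpoint set in Protocol 9.4.1. It does not. That section is a reporting instruction, and the protocol's analysis text for the examinations (10.3.4.2) asks only for listings and descriptive statistics.

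Third, the eCRF is not among the documents. If it asks investigators to mark only changes as clinically significant, few old findings would be counted. That is possible, but the SAP does not say so, and two programmers could reach different counts.

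Fourth, 1:1 randomization makes entry findings similar between arms in expectation, and neither a test nor a decision rule is attached to this count. That stands: the effect is dilution and noise, not systematic bias.

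**Conclusion.** The point holds for one descriptive table and is minor. As written, the SAP 6.6 count has no baseline reference and, read literally, mixes persisting with new or worsened findings. Any treatment difference in it shrinks by the factor 1 − b. How far depends on the unknown share of patients with a persisting finding: slightly at 10%, by half at 50%, almost wholly at 95%. Those shares, the 5% and 15% rates, and the assumption that every baseline finding persists and is rated significant again are illustrative; none comes from the documents. It would therefore go too far to say that the table will mostly reflect the disease mix at entry.

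The point does not extend to the adverse event tables, the TUG analysis or the primary efficacy result.

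**What to change.** Replace the examination sentence in SAP 6.6 with a rule such as: *Patients with a clinically significant physical or neurological finding that is new, or worse than at baseline as defined in SAP 2.5, will be counted by treatment group; findings present at baseline and unchanged will appear in listings only.* A baseline-to-post-baseline shift table by treatment group would serve equally well. If the eCRF already restricts the rating to changes, it is enough to state that in SAP 6.6 and add the split by treatment group.

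Using the SAP 2.5 baseline also settles which examination to compare with when an item was examined at Visit 1 but not repeated at Visit 2. The cost is one sentence and a small amount of programming on examinations already scheduled.
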